8.2 Labeling

Each box of miltefosine contains 56 capsules: 8 packs of blisters, with each blister pack containing 7 capsules. Each box has a preprinted label with a space for the subject's ID number, alpha code, dosing instructions, 24/7 emergency telephone number, storage conditions, precautions, and lot# and expiry date, as follows:

Clinical Study # PLB-MILT-201	Sponsor: Paladin Labs (USA) Inc.			
ID #	Alpha code			
Take 1 capsule times a day wi	th meals			
If medical emergency, call your doc	tor at ()			
Store in original container at room t	emperature			
CAUTION: INVESTIGATIONAL NEW DRUG LIMITED BY FEDERAL LAW TO INVESTIGATIONAL USE.				
Caution: Keep out of the reach of ch	uildren			
Lot # 8J7717	Expiry Date: 10 July 2012			
Manufactured by: Haupt Pharma Ar	nareg GmbH, Regensburg, Germany			

Each blister pack is preprinted with "Impavido 50 mg capsules" as well as other identifying information.

8.2.1 Storage

Medication should be kept out of the reach of children and away from direct sun light, and at temperatures not above 40°C (104°F).

8.2.2 Drug Accountability

The Treating Physician has to account for all used and unused trial supplies and has to complete a Medication Accountability Form. Residual supplies will be destroyed by the Treating Physician as directed. The completed Medication Accountability Form will be returned to the Data-Management Center. The trial medication must not be used outside this protocol.

8.3 Start of Treatment

Treatment should be started within 2 weeks after the completion of screening assessments. Otherwise compliance with eligibility criteria has to be reassessed.

8.4 Administration of Investigational Product (Miltefosine)

Route: Oral administration

Dose: The daily dosage for subjects of body weight 30-45 kg is 100 mg miltefosine (2 capsules Impavido 50 mg). Subjects with a body weight higher than 45 kg receive 150 mg miltefosine daily (3 capsules Impavido 50 mg).

The capsules should be taken with meals. Subjects taking 2 capsules per day should take one capsule with the morning meal and with the evening meal. Subjects taking 3 capsules per day should take one capsule with the morning meal, the noon meal, and the evening meal.

Duration of treatment: 28 days.

8.5 Allocation of Study Treatment to Subject and Compliance

For subjects who will receive 2 capsules per day, the subject will receive a box of medication (56 capsules) at the initiation of therapy which is sufficient for the total treatment period of 28 days. For subjects who will receive 3 capsules per day, the subject will receive a box of medication (56 capsules) at the beginning of therapy that is enough for 18 days of treatment, and will return to the treatment facility after 2 weeks to receive the final 2 week's supply of medication. Compliance with drug administration will be assessed by subject interview and pill count.

8.6 Treatment Modifications and Study Discontinuation

Dose reduction due to AEs: A subject who does not tolerate the planned dosage will go off-treatment. No dose reduction is planned.

Discontinuation of study treatment and withdrawal from protocol for other reasons: A subject may withdraw from the study at any time and for any reason without penalty, if he or she wishes to do so. The Treating Physician may withdraw a subject if continuing participation is believed to be harmful to the subject's well-being or in the event of protocol violations, non-compliance, positive pregnancy test during active treatment, serious intercurrent illness, or apparent failure of efficacy. The sponsor, PI, and IRB have the right to discontinue the investigation at any time.

In the event that the subject withdraws from the study before the completion of the 28 days of treatment, s/he will be asked to come to the clinic for a final assessment including AEs, lesion measurements, vital signs, blood creatinine, and concomitant medication use.

If the subject withdraws during the follow-up period, s/he will be contacted, if possible, and requested to come to the clinic for lesion measurements.

If possible, positive pregnancy should be followed to the end of the pregnancy.

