4.2.2 Contraindications

- Hypersensitivity to the active substance or any of the excipients
- Pre-existing severe damage of liver or kidney function

- Sjögren-Larsson-Syndrome
- Pregnancy and women of childbearing potential who do not use reliable contraception during and up to 3-6 months after treatment

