4.2.3 Warnings and Precautions

Impavido is contraindicated in pregnancy. Women of childbearing potential have to use effective contraception during and up to 3-6 months after treatment. Vomiting/diarrhea are very common/common side effects of therapy with Impavido and can compromise the efficacy of oral contraception. The subject must be informed by her physician of these symptoms and if necessary, suitable alternative methods of contraception must be used.

Subjects with ALT (liver function), serum creatinine, and blood urea nitrogen (BUN) (renal function) 1.25 times above the normal range were generally excluded from the clinical studies. Thus, data from subjects with abnormalities of liver and kidney function are not available.

Treatment with Impavido may lead to an increase in serum creatinine. Kidney function must be evaluated in biweekly intervals. In subjects with clinically significant abnormality in kidney function, monitoring should be continued until normalization.

Gastrointestinal symptoms such as nausea, vomiting, diarrhea, and a feeling of motion sickness are possible side effects of therapy with Impavido. The subjects must be instructed that in case of prolonged persistence of vomiting and diarrhea a sufficient fluid intake must be ensured, to avoid dehydration and consequently the risk of an impaired renal function.

Organ system	Very Common	Common	
	>10% of subjects	1-10% of pts	
Gastrointestinal	Nausea	Motion sickness	
	Vomiting Grade 1-2*	Diarrhea Grade 1*	
	ç	Headache	
Renal	Creatinine elevation		
	Grade 1*		

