4.2.6 Use in Specific Populations

Pregnancy: There are not adequate data on the use of miltefosine in pregnant women. Studies in animals have shown reproductive toxicity. Impavido is contraindicated in pregnancy. Women of childbearing potential have to use effective contraception during and up to 3-6 months after treatment. Vomiting/diarrhea are very common/common side effects of therapy with Impavido and can compromise the efficacy of oral contraception. The subject must be informed by her

physician of these symptoms and if necessary, suitable alternative methods of contraception must be used. The subject has to be advised to immediately contact her physician for pregnancy testing as soon as there is any suspicion of pregnancy. If the test is positive, the physician and subject must discuss the risks associated with this pregnancy.

Nursing mothers: It is not known whether miltefosine is excreted in the milk. Impavido must not be used during lactation; otherwise breast feeding must be stopped.

Geriatric use: Few subjects of age 65 yrs or greater have been included in investigations.

Renal impairment: Subjects with kidney function tests (serum creatinine, BUN) 1.25 times above the normal range were generally excluded from the clinical studies. Thus, data from subjects with mild/moderate/severe abnormalities of kidney function are not available.

Hepatic impairment: Subjects with liver function tests (AST) 1.25 times above the normal range were generally excluded from the clinical studies. Thus, data from subjects with mild/moderate/severe abnormalities of hepatic function are not available.

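### A positive pregnancy test during treatment is only a discretionary ground for withdrawal in section 8.6; no protocol text available for review expressly requires miltefosine to be stopped

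*Combined protocol and SAP*

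**What the plan says.** The relevant paragraph of 8.6 is headed "Discontinuation of study treatment and withdrawal from protocol for other reasons", so it covers stopping the drug as well as leaving the study. It first gives the subject's own right to withdraw, then the physician's: "The Treating Physician may withdraw a subject if continuing participation is believed to be harmful". The further grounds in that sentence include "non-compliance, positive pregnancy test during active treatment, serious intercurrent illness, or apparent failure of efficacy". The paragraph before it deals with intolerance in mandatory terms: "A subject who does not tolerate the planned dosage will go off-treatment". The only other mention of pregnancy in 8.6 concerns outcome: "If possible, positive pregnancy should be followed to the end of the pregnancy".

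The background sections treat pregnancy as a bar to treatment. Section 4.2.2 lists among the contraindications "Pregnancy and women of childbearing potential who do not use reliable contraception during and up to 3-6 months after treatment". Sections 4.2.3 and 4.2.6 both state "Impavido is contraindicated in pregnancy". For a positive test, 4.2.6 adds: "If the test is positive, the physician and subject must discuss the risks associated with this pregnancy".

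The schedule tables in sections 2 and 9 mark pregnancy tests at screening, Days 1, 7, 14 and 28, and Months 3 and 7. The procedure list in 9.3.2 (Days 7 and 14) does not include one. Section 11.1.4 names screening, end of treatment and follow-up.

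**The concern.** Once a pregnancy has been detected during dosing, continuing or stopping a contraindicated drug should not depend on how a physician reads a discretionary list. The section shows that it can write a binding stop, because it does so for intolerance. For pregnancy it does not, and it puts the positive test beside grounds such as non-compliance and lack of efficacy.

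The risk is the protocol's own. Section 4.2.7 introduces its animal findings as seen at exposures similar to clinical ones. It reports embryo- and fetotoxicity in rabbits dosed during organogenesis at 2.4 mg/kg/day and above, against a study dose of about 2.5 mg/kg/day. The rat finding, from 1.2 mg/kg/day, concerns the first 7 days of pregnancy, so it is less relevant to dosing after detection.

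The verb withdraw also merges two decisions: stopping the drug and leaving follow-up. A subject who leaves without a final lesion assessment counts as a failure in the mITT analysis (12.6.3, 12.7.3).

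**Working it through.** **Search for a stop rule.** The protocol states no figure on this point, so the check is mainly textual.

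- 4.2.2, 4.2.3, 4.2.6: contraindication, and a required discussion of risks after a positive test. A stop is implied but not stated.
- 7.1.2 and 9.3.1: a negative test at screening and an eligibility recheck on Day 1. These act before the first dose only.
- 8.2.2: accounting for capsules, with no stop.
- 11.5: records the action taken as none or permanent discontinuation, and assigns neither to pregnancy.
- 11.7: pregnancy between Day 1 and Month 7 is an SAE. This is a classification.
- 11.8: the 24-hour report covers SAEs judged at least possibly related to the drug. It is a reporting duty.
- 14.2: after the eligibility contact, the next set contact between physician and PI is at Day 28 or Week 6, at or after the end of dosing.
- 15.1: the PI reviews and reports on SAEs, with no stop.

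None of these expressly requires dosing to end.

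**Dosing left after a positive test.** Inputs: 28-day course; 100 mg/day (2 capsules) or 150 mg/day (3 capsules), from 8.4; nominal visits on Days 7 and 14, each ±3 days, from the schedule tables; a 56-capsule box at the start, from 8.5. Assumption: the visit day's doses are taken before the result is known.

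| | Positive at Day 7 | Positive at Day 14 |
|---|---|---|
| Days left | 28 − 7 = 21 | 28 − 14 = 14 |
| Share of course | 21/28 = 75% | 14/28 = 50% |
| Days left over the ±3-day window | 28 − 4 = 24 to 28 − 10 = 18 | 28 − 11 = 17 to 28 − 17 = 11 |
| Dose left at 150 mg/day | 21 × 150 = 3150 mg | 14 × 150 = 2100 mg |
| Dose left at 100 mg/day | 21 × 100 = 2100 mg | 14 × 100 = 1400 mg |
| Capsules in hand, 2 per day | 56 − 14 = 42 | 56 − 28 = 28 |
| Capsules in hand, 3 per day | 56 − 21 = 35 | 56 − 42 = 14 |

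A subject on 2 capsules a day receives the whole course on Day 1, so withholding a refill cannot end her dosing. She has to be told to stop.

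**Effect on the analysis sets.** The evaluable population (12.2) needs dosing on at least 25 of the 28 days. A stop at Day 7 or Day 14 gives 7 or 14 days, and at most 17 with the window, so she leaves that population. Any administration qualifies for mITT, so she stays there.

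**How many.** Enrolment is 10-20 a year for 1-5 years, which is 10 × 1 = 10 to 20 × 5 = 100 subjects of both sexes. The number of women of child-bearing potential is not given.

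**The case against.** The best defence is that the protocol handles this in substance. It calls the drug contraindicated in pregnancy in three places, and the risk discussion in 4.2.6 stands in the same paragraph as one of them, so it adds to the contraindication and does not replace it. The discretionary sentence in 8.6 follows the one on the subject's right to withdraw, and can be read as giving the physician authority to remove someone who has not asked to leave. Every Treating Physician also receives the package insert and consent form (9.1), where a stop instruction could well appear; neither was available for this review. Much of this stands. It limits the point to a missing express instruction in the available text. It does not remove the point, because 8.6 is where a site looks for stopping rules and there the matter is left to judgement.

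Three stronger readings are tempting, and the documents support none of them.

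- A reader might infer that the protocol contradicts itself or permits dosing in pregnancy. No passage permits it.
- A reader might infer from 9.3.2 and 11.1.4 that no test is done between Day 1 and Day 28. Both schedule tables mark Days 7 and 14, and those lists are not exhaustive: 11.1.4 also omits the Day 1 test that 9.3.1 requires, and the screening list in 9.2 omits the ECG that 11.1.5 requires. The tables are the more natural source, and the omission is a matter of alignment.
- A reader might take 75% or 50% as the share of fetal exposure that stopping would avoid. The figures count remaining doses only. Drug already taken is eliminated slowly (4.2.7).

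**Conclusion.** The point holds as a missing explicit instruction. Section 8.6 leaves the response to a positive on-treatment pregnancy test to discretion, and no available passage requires miltefosine to stop. At the scheduled Day 7 and Day 14 tests, 75% or 50% of the course is still to be taken. That size assumes that the schedule tables govern testing and that full dosing would otherwise continue. The contraindication text makes continued dosing unlikely with most physicians, and few subjects will be affected. The change is still worth making, because the possible harm is serious and the cost is very small. Sample size is unaffected and no analysis method changes.

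**What to change.** 1. In 8.6, remove the positive pregnancy test from the list of discretionary grounds and add: *If a pregnancy test is positive during treatment, miltefosine must be stopped permanently and at once, no further capsules dispensed, and unused capsules returned to the Treating Physician.*
2. Add that the subject stays in follow-up for safety, pregnancy outcome and lesion assessment, unless she withdraws consent or needs other antileishmanial therapy, which 8.8 allows only off-protocol.
3. As a secondary alignment, list the Day 7 and Day 14 pregnancy tests from the schedule tables in 9.3.2 and 11.1.4.

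The cost is two sentences in 8.6 and one line in each of the other two sections, with no new visits. Sites that follow the tables do no extra tests; a site working only from 9.3.2 would add two per woman of child-bearing potential. The rare affected subject loses her remaining doses and, on a stop at Day 7 or Day 14, her place in the evaluable population, while remaining in mITT. The action field in 11.5 already has the category needed to record the stop.

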11.6 Monitoring and Reporting of Adverse Events

The Treating Physician will monitor subjects for the occurrence of AEs from time the first investigational product is taken on Day 1 through the end of follow up at Month 7 for CL or Month 13 for ML. For the period between Study Day 1 and Study Week 6 (2 weeks after the end of therapy), all AEs regardless of seriousness or relationship to the investigational product are to

be recorded on the CRF. For the period Week 6 to Month 7 for CL, or Month 13 for ML, only AEs requiring medical attention are to be recorded on the CRF.

Whenever possible, symptoms should be grouped as a single syndrome or diagnosis. The Treating Physician should specify the date of onset, maximum severity grade, his/her opinion as to association between the AE and the administration of the investigational product (causality), outcomes including corrective therapy given (if applicable). Clinically significant AEs ongoing at the last follow up visit will be followed to resolution or stabilized including the administration of any concomitant medications.

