12.6.3 Handling of Missing Data

Missing lesion measurements will be ignored when presented as summary statistics of lesion areas and lesion responses as presented by numbers of lesions evaluated at each time point. Subjects who do not provide lesion response measurements at their final scheduled follow up will be considered lesion ane subject failures in the mITT analysis.

Note that if a subject does not appear at the scheduled Study Week 6, Month 3, or Month 7 visits, the subject's estimate of his/her lesion response may be obtained from the subject by telephone, and will be noted as obtained in that manner. Such data is not defined as missing. For such data, the Treating Physician and the PI will jointly decide if the subject's estimate is likely to be reliable. In a single-group non-comparative study such as this one, errors in interpretation will only apply to miltefosine subjects and will not be corrected by being equally applied to a comparator group. Therefore, it is important for subject, physician, and Investigator to avoid two potential errors: 1) erroneously viewing a lesion as healed when in fact it is still present, 2) erroneously viewing a lesion as failed because a subject does not show up for clinic, when in fact the lesion has healed and the subject does not want to spend time coming to clinic.

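### Section 8.6 does not separate stopping miltefosine from leaving the study, so a subject who is withdrawn or not followed and later heals counts as an mITT failure

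*Combined protocol and SAP*

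**What the plan says.** Section 8.6 opens with intolerance: "A subject who does not tolerate the planned dosage will go off-treatment", and no dose reduction is planned. Nothing is said about that subject's later visits. The next paragraph is labelled "Discontinuation of study treatment and withdrawal from protocol for other reasons" but describes only withdrawal. The physician has discretion to remove someone for whom staying in could do harm, and also "in the event of protocol violations, non-compliance, positive pregnancy test during active treatment, serious intercurrent illness, or apparent failure of efficacy". For someone leaving before Day 28, the procedure is that "s/he will be asked to come to the clinic for a final assessment including AEs, lesion measurements, vital signs"; kidney function and other medicines are checked too. A subject who withdraws during follow-up is contacted if possible and asked to attend for lesion measurements. Neither contact is tied to Month 7 or Month 13.

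Section 8.8 treats inability to comply as one reason for removal from the protocol, after which another antileishmanial agent may be given.

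On the analysis side, cure is read at Month 7 for CL (10.1.3, 10.1.4) and Month 13 for ML (10.2.3). Section 12.2 puts everyone who took any dose in mITT. The evaluable set needs at least 25 of 28 dosing days, a final measurement and no rescue. The cure rates in these two populations are the primary endpoints. For CL, 12.6.3 says of the mITT analysis: "Subjects who do not provide lesion response measurements at their final scheduled follow up will be considered lesion ane subject failures". Section 10.1.3 likewise treats missing lesion data as failure, and 12.7.3 has the matching mITT rule for ML. Telephone reports count as non-missing for CL if judged reliable; for ML, a subject's own report of the mucosal examination is not accepted.

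On safety, 11.6 monitors AEs from first dose "through the end of follow up at Month 7 for CL or Month 13 for ML", and 11.7 makes a pregnancy up to Month 7 an SAE.

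**The concern.** The endpoint lies six or twelve months after treatment, but the only assessment 8.6 provides for a subject who leaves during dosing falls at or before Day 28. That assessment cannot stand in for the endpoint, because lesions go on healing after treatment ends. If the subject is not seen or contacted again, the missing-data rule supplies a failure whatever happened to the lesion.

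Two things make this more than a missing detail. First, non-compliance and protocol violation are reasons that need not say anything about healing, yet each can end observation of it. Second, the evaluable set excludes anyone with fewer than 25 dosing days, so mITT is the only primary analysis in which substantially early stoppers appear at all.

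The same subjects may have tolerated the drug worst. After full withdrawal they do not get the AE monitoring to Month 7 or 13 or the pregnancy tests scheduled at Months 3 and 7, although 4.2.7.1 cites a terminal half-life of 31 days.

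**Working it through.** There is no design figure to reproduce: 12.1 gives no sample size calculation and 12.3 makes the analysis descriptive.

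**Step 1: why an early assessment cannot replace the endpoint.** Table 3 (4.2.8.3, Bolivian CL) gives the miltefosine arm as 15/44 = 34% healed at end of treatment and 36/41 = 88% at 6 months after treatment.

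**Step 2: how the rules combine for a subject withdrawn at, say, week 3.**
- In mITT: yes (any dose, 12.2).
- In the evaluable set: no (fewer than 25 days).
- Assessment provided by 8.6: one, at withdrawal.
- Month 7 or 13 measurement: not provided for.
- mITT result if none is obtained: failure (10.1.3 and 12.6.3 for CL, 12.7.3 for ML).
- Escape route: a telephone report for CL, if contact continues; none for ML.

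**Step 3: what the missing-as-failure rule can do to a rate.** Table 1 (4.2.8.2), miltefosine arms:
- Colombia: 40/44 = 90.9% per protocol, 40/49 = 81.6% intent-to-treat; gap 9.3 points from 5 unassessable subjects.
- Guatemala: 20/38 = 52.6% against 20/40 = 50.0%; gap 2.6 points from 2 unassessable subjects.

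These subjects are listed as lost after therapy or later, not as early stoppers, so the figures show scale only.

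**Step 4: size in this study.** Let w be the share of mITT subjects who stop early and have no final outcome, and h the share of those who would be healed at the final visit. Then understatement of the mITT cure rate = w × h.

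Neither quantity is in the documents. I assume w = 2-15%, and h = 20-91%, the span of the Table 1 rates (Guatemalan placebo intent-to-treat to Colombian miltefosine per protocol).

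| w | h = 20% | h = 53% | h = 91% |
|---|---|---|---|
| 2% | 0.4 | 1.1 | 1.8 |
| 5% | 1.0 | 2.7 | 4.5 |
| 10% | 2.0 | 5.3 | 9.1 |
| 15% | 3.0 | 8.0 | 13.7 |

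(percentage points)

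Example: 20 subjects, 2 early stoppers without outcome, 91% cure in the other 18. Missing as failure gives 18 × 0.91 / 20 = 81.9%. If the two were followed, the rate would be (16.38 + 2h) / 20, which is 83.9% at h = 20%, 87.2% at h = 53% and 91.0% at h = 91%.

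**Step 5: weight of one subject.** Section 7.1.1 plans 10-20 subjects a year for 1-5 years, so 10 × 1 = 10 to 20 × 5 = 100 in total. One subject is worth 1/100 = 1 point to 1/10 = 10 points, and more once CL and ML are reported separately, as 12.2 requires.

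**The case against.** The strongest reply is that 8.6 nowhere says that stopping drug ends study participation. Intolerance has its own paragraph and leads only off treatment; the final assessment applies to a subject who withdraws from the study; and physician withdrawal is discretionary. Other sections fit continued follow-up. Section 11.5 records permanent discontinuation as an action on the product, 11.6 makes no exception for subjects off drug, and 12.2 lists dosing days and a final measurement as separate conditions. This stands. A reader might infer that every early stopper loses the final outcome; the text supports only an unstated rule for those off treatment and a possible loss for those withdrawn.

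It is also fair that 12.6.3 accepts telephone data for CL and itself warns against scoring a healed non-attender as failed. That narrows the problem for CL where contact continues. It does nothing for ML.

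On pregnancy, 8.6 asks that a positive pregnancy be followed to its end where possible. What lapses after full withdrawal is detection of a later pregnancy.

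Two tempting uses of the background data fail. The 14/14 cured after 20 days (4.2.8.1) were evaluable subjects in a planned 20-day arm, not early stoppers, and so do not estimate h. A reader might also quote 5-10 points per subject from annual enrolment of 10-20, but 14.4 plans one final analysis and no yearly rate.

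Finally, the missing-data rule is prespecified, lowers the cure rate rather than flattering the drug, and feeds no hypothesis test. That limits the seriousness of the defect but does not remove it.

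**Conclusion.** The point holds as a gap in the follow-up rule with a predictable direction. Section 8.6 allows withdrawal for reasons not tied to outcome and provides no Month 7 or 13 assessment afterwards. It is silent on subjects who only stop drug, so treating physicians may handle them differently. Anyone left without a final measurement is an mITT failure even if healed. The understatement is w × h, about 0.4 to 13.7 points over the assumed ranges; a stated early-stopping rate would narrow that.

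A reader might go further and say that the mITT rate measures retention on drug rather than cure. The documents do not support that: a subject who stops drug but is measured at the final visit is scored on lesion response. Nor do 11.6 and 11.7 flatly contradict 8.6. They can be met for subjects who only stop drug, and lapse only after full withdrawal. As the study is descriptive, this should be corrected but does not undermine the design.

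**What to change.** In 8.6, define stopping miltefosine and leaving the study as separate events. State that subjects who stop drug early for any reason, including non-compliance or protocol violation, are asked to keep the existing Week 6, Month 3, Month 7 and (ML) Month 13 assessments for lesion or MSS, AE and pregnancy data, unless they decline. Leave unchanged the grounds for stopping drug and the physician's ability to remove a subject for harm or lack of efficacy.

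Three additions are needed:
- Reconcile the new text with 8.8, which bars other antileishmanial drugs while on protocol, and with 10.3, so that continued data collection does not block rescue treatment.
- Prespecify how mITT classifies subjects who received other antileishmanial therapy; the plan is silent on a subject healed after rescue.
- Report observed failures separately from failures by missing data, for CL and ML.

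The cost is wording in these sections and in the analysis plan, plus some follow-up effort for early stoppers. The visits are already in the schedule, and telephone contact for CL is already allowed.
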